5.3.1.1 Imaging Assessments

Imaging assessments will be evaluated by the investigator at baseline and every 6 weeks + 7 days counting from C1D1 during the first 24 weeks and then every 12 weeks ± 7 days thereafter until the subject develops radiological disease progression per RECIST v1.1 by local investigator evaluation or starts other systemic anticancer treatment, whichever comes earlier.

All measurable disease must be documented at Screening and re-assessed at each subsequent radiologic evaluation. Imaging will include CT scans with contrast of the thorax, abdomen and pelvis. If the CT scan with contrast is medically not feasible, a CT scan without contrast or MRI may be used for imaging. Bone scans (or focal X-ray) may be performed if metastatic disease in bone is suspected. The same mode of imaging should be utilized throughout the study unless medical necessity requires a change.

Assessment of response using RECIST v1.1 [Eisenhauer et al, 2009] will be based upon local investigator evaluation. Confirmatory scans for CR or PR should be done at least 4 weeks after the date of the scan that CR or PR was first observed.

Response assessments for the primary objective of this trial (ORR) will be made using modified RECIST v1.1. The same measurable and non-measurable lesions determined at baseline will be followed by RECIST v1.1 throughout the study.

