5.3.1.2 Response Criteria Based on Modified RECIST v1.1

For subjects with measurable disease at baseline, the following criteria in [Table 4](#) will be used:

Table 4 Response Criteria Based on Modified RECIST v1.1

Serum Markers	Target Lesions	Non-Target Lesions	New Lesions	Overall Timepoint Response Assessment	
	(target lesion response)	(non-target lesion response)	(unequivocal new lesions)		
Values that fall below the ULN for the assay employed	CR	CR	No or Equivocal	CR	
	CR	Not Applicable	No or Equivocal	CR	
	Not applicable	CR	No or Equivocal	CR	
For both AFP and beta-hCG, no increase \geq 50% in 2 samples at least 1 week apart compared to nadir values, at least one of the values are above ULN	CR	CR	No or Equivocal	PR	
	CR	Not Applicable	No or Equivocal	PR	
	Not applicable	CR	No or Equivocal	PR	
For both AFP and beta-hCG, no increase \geq 50% in 2 samples at least 1 week apart compared to nadir values	CR	Non-CR/Non-PD	No or Equivocal	PR	
	CR	NE/ND	No or Equivocal	PR	
	PR	CR	} = not PD	No or Equivocal	PR
	PR	Non-CR/Non-PD		No or Equivocal	PR
	PR	NE/ND		No or Equivocal	PR
	PR	Not applicable		No or Equivocal	PR
For both AFP and beta-hCG, no increase \geq 50% in 2 samples at least 1 week apart compared to nadir values	SD	CR	} = not PD	No or Equivocal	SD
	SD	Non-CR/Non-PD		No or Equivocal	SD
	SD	NE/ND		No or Equivocal	SD
	SD	Not applicable		No or Equivocal	SD
Any	PD	Any	Any	PD	
Any	Any	PD	Any	PD	
Any	Any	Any	Yes or Unequivocal	PD	
Increase \geq 50% in serum tumor markers AFP or beta-hCG in 2 samples at least 1 week apart compared to nadir values	Any	Any	Any	PD	
NE/ND	NE/ND	Not PD	No or Equivocal	NE	

CR: complete response; ND: not done; NE: non-evaluable; PD: progressive disease; PR: partial response; SD: stable disease.

Confirmatory assessment for CR or PR should be done at least 4 weeks after the date of the CR or PR was first observed.

In subjects whose only evidence of disease is elevated serum tumor markers ($> 2 \times$ ULN AFP or $> 2 \times$ ULN β hCG) at baseline, the modified RECIST v1.1 will reduce to serum tumor marker response criteria described in Section 5.3.1.3. In subjects whose only evidence of disease is elevated serum tumor markers ($> 2 \times$ ULN AFP or $> 2 \times$ ULN β hCG) at baseline, confirmatory assessment for CR or PR is not required.

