5.3.1.3 Response Criteria Based on Serum Tumor Biomarkers

Blood will be drawn for the measurement of serum AFP and serum β hCG at day 1 of every cycle and during the post treatment period follow up period to align with imaging assessment (every 6 weeks + 7 days counting from C1D1 for the first 24 weeks and then every 12 weeks ± 7 days thereafter) until the subject develops radiological disease progression per RECIST v1.1 by local investigator evaluation or starts other systemic anticancer treatment. To evaluate the effect of ASP1650 on changes in serum β hCG and AFP, disease response will be derived for subjects with elevated serum tumor markers ($> 2 \times$ ULN AFP or $> 2 \times$ ULN β hCG) at baseline using the following definition:

- CR is defined as values that fall below the ULN for the assay employed. Confirmed CR must remain at that level for at least 4 weeks.
- PR is defined by serum tumor markers (AFP and β hCG) that are decreasing. Elevated serum tumor markers (AFP or β hCG) values must fall $\geq 90\%$ below baseline pretreatment levels for β hCG or 50% decrease below baseline pretreatment levels for AFP. PR must persist for at least 6 weeks to be a confirmed PR. If both tumor markers are elevated and 1 falls below 90%, the other should fall at least below 50% of baseline pretreatment levels.
- Stable disease (SD) is defined as no change or a change in serum tumor biomarkers that does not qualify as CR, PR or PD. Durable SD is defined as SD that is maintained for at least 12 weeks.
- PD is defined as $\geq 50\%$ increase in AFP or β hCG in 2 samples, 1 week apart compared to nadir.

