7.1 Sample Size

The sample size for the Safety Lead-in phase is not based on a statistical power calculation. The planned number of up to 18 subjects would provide adequate information for the objectives of the safety cohort.

Simon's optimal 2-stage design [Simon, 1989] will be used for conducting phase 2 of the study. The null hypothesis is that the true ORR is 10%, and the alternative hypothesis is that the true ORR is 25%. The study will be carried out in 2 stages. In stage I, a total number of 13 subjects treated at the RP2D will be evaluated.

If there is 1 or fewer responses among these 13 subjects, the study will be stopped early for futility. Otherwise, an additional 21 subjects will be enrolled in stage II, resulting in a total number sample size of 34. If there are 6 or more responses among these 34 subjects, we reject the null hypothesis and claim that the treatment is promising. The design controls the type I error rate at 10% and yields the power of 80%.

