In subjects whose only evidence of disease is elevated serum tumor markers ($> 2 \times$ ULN AFP or $> 2 \times$ ULN β hCG) at baseline, the modified RECIST v1.1 will reduce to serum tumor marker response criteria. Serum marker criteria can be found in section 5.3.1.3 of the protocol. In subjects whose only evidence of disease is elevated serum tumor markers ($> 2 \times$ ULN AFP or $> 2 \times$ ULN β hCG) at baseline, confirmatory assessment for CR or PR is not required.

Best overall response is determined once all tumor response data for the subject is available. Subjects will be classified by best response on study as outlined in modified RECIST v1.1 criteria. For best overall response of stable disease (SD), SD must be documented as present at least once after study entry and maintained for at least 12 weeks.

ORR as assessed by RECIST 1.1 alone and by serum marker alone will be performed as a sensitivity analysis.

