5.2.3 Progression-Free Survival (PFS)

PFS is defined as the time from the date of first dose until the date of disease progression as assessed by modified RECIST 1.1, or until death due to any cause. If a subject has neither progressed nor died, the subject will be censored at the date of last disease assessment or at the date of registration if no post-baseline radiological assessment is available. Subjects who receive any further anticancer therapy for the disease before disease progression will be censored at the date of the last disease assessment before the anticancer therapy started. If progression or death occurs after missing 2 scheduled disease assessments, the subject will be censored at the date of last disease assessment or at the date of registration if no post-baseline disease assessment is available. A subject has missed 2 scheduled disease assessments if the gap between two disease assessments is more than 2.5 times the scheduled disease assessment interval. During treatment, this will be 105 days (2.5 x 42 days during treatment for the first 24 weeks); during the follow-up period this will be 210 days (2.5 x 84 days during follow-up).

PFS (in days) is calculated as:

(Date of death, or Progression assessed by modified RECIST 1.1, or censoring) – (Date of first dose) +1.

To apply the cut-off date to PFS is to exclude disease assessments, death and anti-cancer therapy date after cut-off date in the analysis.

Note: Patient cannot be censored at “Not Evaluable (NE)”. If NE is the only previous assessment, then PFS will be censored at Day 1.

PFS will be calculated for each subject using RECIST 1.1 alone, and serum markers alone.

Table 3 PFS Definition

Situation	Date of Event or Censor	Outcome
No evaluable post-baseline efficacy assessments, no death	Date of first dose	Censor
Subject did not receive new anti-cancer therapy:		
Disease progression documented per modified RECIST v1.1	Date of PD	Event
No disease progression, but death recorded on eCRF	Date of death	Event
No PD nor death	Date of last efficacy assessment or at the date of first dose if no postbaseline efficacy assessment is available	Censor
Subject received new anti-cancer (ACT) therapy:		
Disease progression documented per modified RECIST v1.1 after new ACT	Date of last efficacy assessment before start of new anti-cancer therapy or at the date of first dose if no post-baseline efficacy assessment is available	Censor

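### In marker-only subjects an unequivocal new lesion is not progression by modified RECIST, which distorts modified-RECIST PFS and DOR and, more narrowly, ORR, the futility count and CBR

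*Protocol*

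**What the plan says.** Inclusion criterion 11 (Protocol 3.2) admits a subject on a rising marker without measurable disease. Protocol 5.3.1.2 then treats two groups differently.

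- **Measurable disease at baseline.** Table 4 applies. One of its rows makes an unequivocal new lesion PD whatever the markers and other lesions show.
- **Marker-only disease (AFP or βhCG above 2 × ULN).** Here "the modified RECIST v1.1 will reduce to serum tumor marker response criteria described in Section 5.3.1.3", and confirmation of CR or PR is waived.

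In Protocol 5.3.1.3 all four categories are defined by AFP and βhCG. PD is a rise of at least 50% "in 2 samples, 1 week apart compared to nadir". Imaging is not mentioned in any of the definitions. SAP 5.1.1 carries the rule over: "the modified RECIST v1.1 will reduce to serum tumor marker response criteria. Serum marker criteria can be found in section 5.3.1.3 of the protocol".

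Imaging is scheduled for all subjects (Protocol 5.3.1.1) "until the subject develops radiological disease progression per RECIST v1.1 by local investigator evaluation or starts other systemic anticancer treatment". Protocol 5.3.1.3 ends marker sampling on the same terms. Protocol 6.1 lists marker progression or radiological progression as a reason to stop treatment in any subject, but lets the investigator continue treatment up to 12 cycles.

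For the time-to-event endpoints, SAP 5.2.2 and 5.2.3 take progression from modified RECIST. SAP 5.2.3 adds: "If a subject has neither progressed nor died, the subject will be censored at the date of last disease assessment".

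**The concern.** Disease first detected by markers can later become visible on CT, and these subjects are scanned on the common schedule. The plan will therefore collect evidence of radiological progression in marker-only subjects that its main response criteria have no means of using. The same scan is PD in one subject and nothing in another, depending only on how disease was documented at baseline.

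Two things are at stake. Modified-RECIST PFS and DOR may treat a documented progression as no event, and the censoring that follows is informative because it is tied to the progression. The primary endpoint may also include a marker response that first appears after new metastases. Both errors favour the drug.

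**Working it through.** **1. The rules side by side**

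| Finding: unequivocal new lesion, no qualifying marker rise | Measurable disease at baseline | Marker-only at baseline |
|---|---|---|
| Governing text | Protocol Table 4 / SAP Table 1 | Protocol 5.3.1.3 |
| Timepoint response by modified RECIST | PD | CR, PR or SD, as the markers show |
| Modified-RECIST PFS and DOR | Event at scan date | No event |
| Reason to stop treatment (Protocol 6.1) | Yes | Yes |

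**2. PFS and DOR**

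Suppose a marker-only subject has a new lesion on the week 6 CT and no marker PD.

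- If he stops treatment, post-treatment scans and markers also stop, because radiological progression ends that schedule. No later marker PD can then be seen, and he is censored at his last assessment.
- If he starts new anticancer therapy, SAP Table 3 censors PFS at the last assessment before it, even if he later dies.
- If he stays on treatment, markers are drawn on day 1 of each cycle and a marker PD can still be recorded, but later than the lesion.
- A death counts as a PFS event only if neither new therapy nor two missed assessments come first. SAP Table 2 lists only PD as a DOR event, although the formula above it also names death.

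In each case the lesion itself is not an event.

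**3. ORR, futility count and CBR**

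The order of events decides.

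- *Marker PR at week 4, new lesion at week 6.* Confirmation is waived, so the PR already stands as best response. A new-lesion rule would not remove it.
- *New lesion at week 6, treatment continued, AFP first down by 50% at week 8 (cycle 5 day 1).* Under 5.3.1.3 this is a PR and counts. Under a new-lesion rule it would not.
- *If the confirmed-response wording of Protocol 2.3.1 governs instead of the waiver,* a PR must persist for 6 weeks (5.3.1.3). A PR before the lesion could then be confirmed after it.
- *CBR.* Marker SD reaching 12 weeks counts even if a lesion appeared at week 6.

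**4. The plan's design, reproduced**

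Inputs from Protocol 7.1: null ORR 10%, alternative 25%. The rules are "If there is 1 or fewer responses among these 13 subjects, the study will be stopped early for futility" and "If there are 6 or more responses among these 34 subjects, we reject the null hypothesis".

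P(success) = Σ over x ≥ 2 of P(X₁ = x) · P(X₂ ≥ 6 − x), with X₁ ~ Bin(13, p) and X₂ ~ Bin(21, p).

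At p = 0.10:

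- P(stop) = 0.9¹³ + 13 × 0.1 × 0.9¹² = 0.2542 + 0.3672 = 0.621, so P(continue) = 0.379.
- P(success) = 0.2448×0.1520 + 0.0997×0.3516 + 0.0277×0.6353 + 0.0055×0.8906 + smaller terms = 0.0957.

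At p = 0.25, P(success) = 0.811. Both agree with the stated 10% and 80%.

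**5. One miscounted responder, true ORR 10% in the others**

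| Miscounted subject in | Formula | P(continue) | P(success) |
|---|---|---|---|
| None | as above | 0.379 | 0.096 |
| Stage I | 12 others in stage I, at least 1 needed: 1 − 0.9¹² = 1 − 0.2824 | 0.718 | 0.216 |
| Stage II | 20 others in stage II, total of 5 needed from the rest | 0.379 | 0.171 |

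One subject is 1/34 = 2.9 percentage points.

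**6. As a rate (assumptions only)**

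Let s be the marker-only share and q the proportion of their true non-responders who are miscounted. The effective null rate is 0.10 + s × 0.90 × q.

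| s | q | Effective rate | P(success) |
|---|---|---|---|
| 5% | 5% | 10.2% | 0.104 |
| 10% | 10% | 10.9% | 0.130 |
| 20% | 10% | 11.8% | 0.169 |
| 30% | 20% | 15.4% | 0.361 |

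The documents give neither s nor q.

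**The case against.** The strongest reply has four parts.

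- **Modified RECIST is described as incorporating RECIST v1.1 (Protocol 5.3.1), so a new lesion could be implied to be PD.** This does not stand. The general description yields to the specific rule that, in this subgroup, the criteria reduce to the marker section.
- **Radiological progression is already a reason to stop treatment.** True, but that is a treatment rule. It feeds neither response nor the PFS or DOR event.
- **Other analyses show the discordance.** This stands in part. SAP 5.2.3 derives PFS by RECIST v1.1 alone for each subject, and a new lesion is progression there. Marker-only responses also cannot inflate the ORR by RECIST v1.1. However, Protocol 5.3.1 confines RECIST-alone response assessment to subjects with measurable disease, so it is unclear whether marker-only subjects are covered. Neither analysis repairs the modified-RECIST endpoints.
- **The effects on ORR and on PFS partly exclude each other.** This stands. If sampling stops at the lesion, hardly any new marker response can follow. If it continues on treatment, marker PD can still be found. One subject will rarely distort all four endpoints.

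A reader might infer that any marker-only subject with new metastases is wrongly counted as a responder, or can never reach a PFS event. The documents support neither. A response recorded before the lesion counts under ordinary best-response rules, and marker PD or death may still follow.

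**Conclusion.** The gap is real and lies in the plain text of both documents. The firm consequence is for modified-RECIST PFS and DOR in marker-only subjects: a new lesion is not an event, and the time may be censored unless marker PD or, for PFS, a countable death follows. These are secondary endpoints summarised by Kaplan-Meier without a test.

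The consequence for ORR, the futility count and CBR is conditional. It needs a marker CR or PR first recorded (or confirmed, if that wording governs) at or after the lesion, or durable marker SD running past it. With cut-offs of 2/13 and 6/34 one such subject can decide either look, and the illustration gives 0.216 or 0.171 against 0.096. Those figures assume that exactly one miscount occurs; nothing in the documents says how often it would. A claim that the type I error is inflated to a particular value is therefore not supported.

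Severity: should be fixed, and before the futility count and the final response data are read.

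**What to change.** In Protocol 5.3.1.2 and 5.3.1.3, and in SAP 5.1.1 and Tables 2 and 3, state that for modified RECIST:

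1. An unequivocal new lesion on imaging is PD at the date of that scan in every subject, marker-only subjects included, whatever the markers show.
2. That date is the PD event for modified-RECIST PFS and DOR.
3. A marker CR, PR or SD first recorded at or after that date does not count towards best overall response, ORR or CBR.

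Two clarifications belong with it: say whether the RECIST-alone analyses include marker-only subjects, and whether the confirmation waiver or the confirmed-response definition governs them. The serum-marker-alone sensitivity analysis stays as it is.

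The cost is a few sentences. CT is already scheduled, and the sample size and decision rules do not change (34 subjects, type I error 0.096, power 0.811). Observed ORR, CBR, DOR and PFS may be slightly less favourable.

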5.3.1.3 Response Criteria Based on Serum Tumor Biomarkers

Blood will be drawn for the measurement of serum AFP and serum β hCG at day 1 of every cycle and during the post treatment period follow up period to align with imaging assessment (every 6 weeks + 7 days counting from C1D1 for the first 24 weeks and then every 12 weeks ± 7 days thereafter) until the subject develops radiological disease progression per RECIST v1.1 by local investigator evaluation or starts other systemic anticancer treatment. To evaluate the effect of ASP1650 on changes in serum β hCG and AFP, disease response will be derived for subjects with elevated serum tumor markers ($> 2 \times$ ULN AFP or $> 2 \times$ ULN β hCG) at baseline using the following definition:

- CR is defined as values that fall below the ULN for the assay employed. Confirmed CR must remain at that level for at least 4 weeks.
- PR is defined by serum tumor markers (AFP and β hCG) that are decreasing. Elevated serum tumor markers (AFP or β hCG) values must fall $\geq 90\%$ below baseline pretreatment levels for β hCG or 50% decrease below baseline pretreatment levels for AFP. PR must persist for at least 6 weeks to be a confirmed PR. If both tumor markers are elevated and 1 falls below 90%, the other should fall at least below 50% of baseline pretreatment levels.
- Stable disease (SD) is defined as no change or a change in serum tumor biomarkers that does not qualify as CR, PR or PD. Durable SD is defined as SD that is maintained for at least 12 weeks.
- PD is defined as $\geq 50\%$ increase in AFP or β hCG in 2 samples, 1 week apart compared to nadir.

5.3.2 Immunogenicity Assessments

Serum samples to assess the formation of anti-drug antibodies against ASP1650 will be collected as outlined in the Schedule of Assessments Table 1. Blood sampling, processing, storage and shipment instructions will be provided in the Laboratory Manual. Samples will be shipped to and analyzed by a sponsor designated analytical laboratory using validated analytical methods. Refer to the Laboratory Manual for more detailed information.

5.4 Safety Assessment

5.4.1 Vital Signs, Height and Weight

Vital signs will include systolic and diastolic blood pressure (mmHg), radial pulse (beats/min) and temperature. All vital signs will be measured in a consistent manner (with the subject in the sitting or supine position) throughout study participation.

Height and weight will be measured using standard institution practice and equipment.

If clinically significant vital sign changes from baseline (pretreatment) are noted, the changes will be documented as AEs on the AE page of the eCRF. Clinical significance will be defined as a variation in vital signs, which has medical relevance as deemed by the investigator that could result in an alteration in medical care. For clinically significant vital sign changes, the investigator will continue to monitor the subject until the parameter returns to grade ≤ 1 , or to the baseline (pretreatment) value, or until the investigator determines that follow up is no longer medically necessary.

5.4.2 Observation Period Following ASP1650 Infusion

Following the first dose of ASP1650 on C1D1, the subject must be observed for 2 hours post ASP1650 infusion. If AEs are observed during this time, subsequent ASP1650 infusion times should be extended and subjects should continue to be observed for 2 hours post ASP1650 infusion. If the subject does not develop any AEs, the subject should be observed for 1 hour post-infusion for their subsequent ASP1650 infusions. The subject should be instructed to notify site personnel if they develop any AEs during this observation time period.

In the event of grade 3 or 4 IRRs, additional samples should be collected as follows:

- Once the subject has been stabilized, blood for cytokine/chemokine panel should be collected for shipment to central laboratory
- If any symptoms of potential anaphylaxis are observed, samples for tryptase should be collected for shipment to the central laboratory

In addition, due to the presence of the excipient trehalose (disaccharide) and dilution of ASP1650 with sterile 5% Dextrose Injection, a glucose check via finger prick at 1 hour post-infusion will be performed on Day 1 of all cycles. If a glucose check via finger prick is not available, glucose check via blood sampling is acceptable.

5.4.3 Laboratory Assessments

Below is a table of the laboratory tests that will be performed during the conduct of the study. See Schedule of Assessments [Table 1](#) for study visit collection dates. All laboratory tests must be sent to the central laboratory for analysis.

Central laboratory results should be used to confirm eligibility, however if repeat screening labs are required, local laboratory results can be used to confirm eligibility. The screening labs used to determine eligibility should be collected within 14 days prior to C1D1. In situations where laboratory results are outside of the permitted range, the investigator may

opt to retest the subject and subsequent within range screening central lab results may be used to confirm eligibility. In case of multiple central laboratory data within the Screening period, the most recent data should be used to confirm eligibility. Subjects requiring transfusions to meet eligibility criteria are not eligible.

Laboratory tests will be reviewed by the investigator prior to any study treatment. In the event that the central laboratory results are not available in time for treatment decisions, local certified laboratory tests may be used.

Holidays and weekends should be taken into account when scheduling these assessments.

Additional assessments may be done centrally or locally to monitor AEs or as clinically indicated. Clinical significance of out-of-range laboratory findings is to be determined and documented by the investigator/subinvestigator who is a qualified physician.

Panel/Assessment	Parameters to be Analyzed
Hematology	Hematocrit (Hct) Hemoglobin (Hgb) Red Blood Cell Count (RBC) White Blood Cell Count (WBC) WBC differential Absolute Neutrophil Count (ANC) Platelets Mean Corpuscular Volume (MCV) Mean Corpuscular Hemoglobin (MCH) Mean Corpuscular Hemoglobin Concentration (MCHC)
Biochemistry	Albumin Blood Urea Nitrogen (BUN) Calcium Bicarbonate Chloride Creatinine Estimated glomerular filtration rate Glucose Magnesium Phosphate Potassium Sodium Total Bilirubin Total Protein Alanine Aminotransferase (ALT) Alkaline Phosphatase (ALP) Aspartate Aminotransferase (AST) Amylase Lipase
Table continued on next page	

Panel/Assessment	Parameters to be Analyzed
Urinalysis	Color Clarity/turbidity pH Specific gravity Glucose Ketones Nitrites Leukocyte esterase Bilirubin Urobilinogen Blood Protein Microscopic urinalysis to be performed if abnormal dipstick
Grade 3 or 4 IRR	Cytokine/Chemokine Panel*
Any reaction with features of anaphylaxis	Serum Total Tryptase*
Biomarkers	Alpha-fetoprotein (AFP) Beta human chorionic gonadotropin (β hCG)
Coagulation	Prothrombin time (PT) (sec) Partial Thromboplastin Time (PTT) International normalized ratio (INR)
Thyroid Function Test	Thyroid stimulating hormone (TSH) Free T4 (thyroxine)

*as applicable

